2.4 Cannabis withdrawal syndrome: Abrupt discontinuation of CB1R agonists in cannabinoid dependent animals or the administration of CB1R antagonist to cannabinoid dependent animals leads to a withdrawal syndrome (86-91). In humans, a cannabis withdrawal syndrome has been reported from retrospective self-report studies (72), prospective outpatient studies (73, 74), and human laboratory studies involving the administration and discontinuation of cannabinoids (49, 50, 75, 76). The typical withdrawal symptoms include anger, aggression, appetite change, weight loss, irritability, anxiety, restlessness, altered sleep, strange dreams, cannabis craving and physical discomfort (11, 49, 50, 73, 75, 77-80). Most symptoms appear within 1 day of abstinence, peak within 2–3 days, and typically resolve within 1–2 weeks. However, other studies (73, 80) suggest that withdrawal symptoms may persist longer than 4 weeks, and specifically sleep disturbances may persist for longer (92-94). Characteristic of a true withdrawal syndrome, abstinence symptoms occur with blind discontinuation and resolve with CB1R agonist re-administration (49, 75, 77, 81, 82). Avoidance of CWS might be one factor that contributes to the persistence of chronic cannabis use, and thus, medications that attenuate CWS may also improve treatment outcomes among individuals with CUD.

2.5 Sleep disturbances are an important manifestation of cannabis withdrawal: Several lines of experimental evidence suggest a role of CB1R in sleep (95, 96); therefore, it is not surprising that sleep disturbance is a common symptom of cannabis withdrawal and is clinically meaningful. About 76% of daily cannabis users who abruptly discontinue the use of cannabis report sleep disturbance (92, 93, 97). Difficulty sleeping and strange dreams have been reported with high cross-study reliability (92). These generally occur within 24 to 72 hours of discontinuation of cannabis use and persist for 6–7 weeks (93, 98). Resumption of cannabis use or administration of oral THC improves sleep or even reinstitutes subjectively normal sleep (66, 99-102). Sleep disturbance is reported as a reason why individuals resume smoking cannabis (103) or use alcohol, sedative/hypnotic drugs, or illicit drugs in attempts to treat their sleep disturbance (98, 104). Similarly, certain drugs of abuse may be more rewarding in insomniacs (105), and preferred to a greater degree in persons who are sleep-restricted or deprived (106-108).

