There are significant problems to accurately measuring the amount of cannabis exposure. Cannabis and cannabinoids may be used by smoking, vaping or per orally. Even within smoking, cannabis and cannabinoids may be smoked as joint, blunt, bowl, etc. There are no standard units of consumption: joints come in different shapes and sizes. The potency (THC content) and the THC:CBD ratio can vary considerably. Finally, urine toxicological estimation of exposure is also fraught with challenges, especially if abstinence is not the goal. Given these challenges to measuring amount of use, self-reported frequency of use has been chosen as an endpoint.

Specifically, the *change* from baseline to the last 4 weeks of the treatment phase in the average number of occasions per day of self-reported consumption of cannabis and cannabinoids captured using the daily TLFB data collected during CAROMA calls. A cannabis use occasion is defined as every time a participant initiates the use of cannabis. This will differ based on the method of use (see below). For example, if a participant uses blunts, or joints, every time he/she lights the joint, will be counted as one occasion. Baseline is defined as the last two weeks before the second screening visit; specifically, this is the TLFB capturing last week use done at the day -7 screening visit and the day of randomization.

Method of Use	Definition of Occasion of Use			
Joint, blunt, roach, etc.	Every time a joint is lit and used = a new occasion			
Bong	Every time a bong is prepared for use, and used			

Table 9: Defining an Occasion of Cannabis Use

Bowl Every time a bowl is packed and used = a	a new occasion
---	----------------

4.2.2 Secondary Endpoints:

- To evaluate the safety and tolerability of 4 mg PF-04457845 QD x 8 weeks in cannabis use disorder patients as indexed by the % of participants who a) experience at least 1 treatment-emergent related and/or possibly related adverse event, b) meet the markedly abnormal criteria for safety laboratory tests at least once post-dose, or c) who meet the markedly abnormal criteria for vital sign measurements at least once post-dose.
- 2) To evaluate whether over the 8 weeks of treatment 4 mg PF-04457845 QD is superior to placebo in reducing cannabis use as measured by amount (grams) used per week (TLFB).

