11.1.2 Cannabis Withdrawal Symptoms: The typical withdrawal symptoms in humans include: cannabis craving, anger, aggression, appetite change, weight loss, irritability, anxiety, restlessness, altered sleep, strange dreams and physical discomfort (39, 40, 99, 225). Less common symptoms include: chills, depressed mood, stomach pain and sweating. Most symptoms appear within 1 day of abstinence, peak within 2–3 days, and resolve within 1–2 weeks. Two studies evaluated symptom time course for at least four weeks (45 days and 28 days, respectively). Both studies observed prominent withdrawal symptoms during the initial two to three weeks of abstinence, some of which persisted through the entire study period (63, 70). The findings of these studies suggest that withdrawal symptoms may persist longer than 4 weeks. Characteristic of a true withdrawal syndrome, abstinence symptoms occur with blind discontinuation and resolve with CB1R agonist re- administration. Finally, the administration of cannabis or THC attenuates withdrawal symptoms.

These symptoms that people experience when they stop smoking marijuana are uncomfortable but not life threatening. The marijuana withdrawal symptoms will be monitored closely. If intolerable, participants will be able to withdraw from further study participation.

11.1.3 Phlebotomy: Bruising, infection and thrombosis can occur during phlebotomy. These risks can be minimized by having these procedures performed by experienced personnel using good clinical technique. Participants will have no more than 3 oz. of blood drawn over the entire study period. These amounts are well within the Red Cross blood standards.

11.1.4 Behavioral/Cognitive Testing: Some participants may experience the behavioral as boring or frustrating. Trained research staff will work closely with participants and if necessary provide them with breaks.

11.2 Known Potential Benefits: Study participation may facilitate a reduction of cannabis use for study participants. Group data collected from this study will also inform the development of

this drug for the treatment of CUD, for which there are no currently approved pharmacological treatments.

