12.0 ADVERSE EVENT REPORTING

An AE is defined as any untoward medical occurrence in a clinical investigation participant administered a drug; it does not necessarily have to have a causal relationship with this treatment. An AE can therefore be any unfavorable and unintended sign (e.g., a clinically significant abnormal laboratory value), symptom, or disease temporally associated with the use of a drug whether or not it is considered related to the drug. All observed or volunteered AEs regardless of treatment group or suspected causal relationship to the investigational product(s) will be reported as described in the following sections.

The site principal investigator will be responsible for monitoring the data and assuring protocol adherence. At a minimum of every six months (including when re-approval of the protocol is sought), each site should notify the Coordinating Center of all adverse events. The Coordinating Center will then conduct safety reviews across all sites participating in the study. During the review process, the study principal investigator and coordinating physician investigator (responsible for medical oversight) will evaluate whether the study should continue unchanged, require modification/amendment, continue or close to enrollment. Either the study principal investigator or institutional review boards overseeing the study have the authority to stop or suspend the study or require modifications.

For all AEs, the investigator must pursue and obtain information adequate both to determine the outcome of the AE and to assess whether it meets the criteria for classification as an SAE requiring immediate notification to the Coordinating Center. For all AEs, sufficient information should be obtained by the investigator to determine the causality of the AE. The investigator is required to assess causality. Follow-up by the investigator may be required until the event or its sequelae resolve or stabilize at a level acceptable to the investigator, and the Coordinating Center concurs with that assessment.

As part of ongoing safety reviews conducted by the Coordinating Center, any non-serious adverse event that is determined by the Coordinating Center to be serious will be reported by the Coordinating Center as a SAE. To assist in the determination of case seriousness further information may be requested from the investigator to provide clarity and understanding of the event in the context of the clinical trial.

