12.1 Reporting Period: For SAEs, the active reporting period begins from the time that the participant provides informed consent, which is obtained prior to the participant's participation in the study, through the last follow up visit (end of study visit). Should an investigator be made aware of any SAE occurring any time after the active reporting period, it must be promptly reported.

12.2 Capturing Adverse Events: Safety and adverse events will be captured using the Systematic Assessment for Treatment Emergent Events (SAFTEE) general and specific inquiry forms, which take approximately 20 minutes to administer. Collection of adverse events will commence from the time the participant signs the informed consent to participate in the study and will continue until the last safety follow up visit. At each study visit, the investigator will

assess whether any subjective AEs have occurred. A neutral question, such as "How have you been feeling since your last visit?" may be asked. Participants may report AEs occurring at any other time during the study. All participants experiencing AEs, whether considered associated with the use of the study drug or not, must be monitored until the symptoms subside and any clinically relevant changes in laboratory values have returned to Baseline or until there is a satisfactory explanation for the changes observed. All AEs will be documented, whether or not the investigator concludes that the event is related to the drug treatment. Any medical condition that is present at the time that the participant is screened will be considered as baseline and not reported as an AE. However, if the study participant's condition deteriorates at any time during the study, it will be recorded as an AE.

The following information will be documented for each event:

- 1. Event term.
- 2. Start and stop date and time.
- 3. Pattern of AE (Frequency).
- 4. Intensity.
- 5. Investigator's opinion of the causal relationship between the event and administration of study drug(s) (related or not related).
- 6. Investigator's opinion of the causal relationship to study procedure(s), including the details of the suspected procedure.
- 7. Action concerning study drug.
- 8. Outcome of event.
- 9. Seriousness.

The different categories of intensity (severity) are characterized as follows:

- Mild: The event is transient and easily tolerated by the participant. The event does not
 generally interfere with usual activities of dailyliving.

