 intensity of the diagnosis, signs/symptoms, or laboratory value on the last day of the
 observed study period has got worse than when it started; is an irreversible congenital
 anomaly; the participant died from another cause with the particular AE state remaining
 "not recovered/not resolved".
- Resolved with sequelae the participant recovered from an acute AE but was left with permanent/significant impairment (e.g., recovered from a cardiovascular accident but with some persisting paresis).
- Fatal the AEs are considered as the cause of death.
- Unknown the course of the AE cannot be followed up due to hospital change or residence change at the end of the participant's participation in the study.

The overall principal investigator will conduct a review of all adverse events upon completion of every study participant. The principal investigator will evaluate the frequency and severity of the adverse events and determine if modifications to the protocol or consent form are required.

12.5 **Pre-Existing Conditions:** Pre-existing conditions, present at the time of signing informed consent, are considered to be concurrent medical conditions and should not be recorded as adverse events. All pre-existing conditions and their severity need to be documented at the time of the screening visit. If the participant experiences a worsening or complication of such a concurrent medical condition, the worsening or complication should be recorded appropriately as an adverse event. Investigators should ensure that the event term recorded captures the change in the condition.

12.6 Worsening of Adverse Events: If the participant experiences a worsening or complication of an AE after the first administration of study drug or any change in study drug, the worsening or complication should be recorded as a new AE. Investigators should ensure that the AE term recorded captures the change in the condition (e.g., "worsening of...").

12.7 Serious Adverse Events: An SAE is defined as any untoward medical occurrence that at any dose:

- 1. Results in death.
- 2. Is life threatening.
 - The term "life threatening" refers to an event in which the participant was at risk of death at the time of the event; it does not refer to an event that hypothetically might have caused death if it were more severe.
- 3. Requires inpatient hospitalization or prolongation of existing hospitalization.
- 4. Results in persistent or significant disability/incapacity.

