14.2.2 Secondary Outcomes: The same analytic strategy will be followed for secondary outcomes compared to the primary outcome. Primary analyses will be based on ANCOVA with multiple imputation on the modified intent-to-treat sample, secondary analyses will include mixed models, tipping point analyses and analyses of the per protocol sample. The emphasis will be on effect estimation. Testing in the primary analyses will be adjusted using the Bonferroni-Holm method. For each eCB, plasma levels will be assessed by fitting a mixed effects model with treatment, time, site, and the interaction terms as fixed effects, and tobacco use as covariate. Exploratory analyses will be conducted to assess the effect of variables such as gender and use of other substances on endocannabinoids. Since we expect floor effects for the blood levels of PF-04457845 in the placebo condition, PF-04457845 blood level will be assessed by using non-parametric models (226, 227) with treatment, time, site, and the interaction terms as factors.

14.3 Safety Analysis: The review and summary of safety will be performed on the modified intent-to-treat sample. Events or abnormalities will be searched from the time of the first dose until 5 half-lives after the last dose. Clinical laboratory data will be summarized quantitatively using descriptive statistics such as changes from baseline summarized by mean, standard deviation, median, minimum and maximum, and summarized qualitatively by tabulating clinical abnormalities. Vital signs, BMI, weight will be summarized using descriptive statistics. Group differences in the percentage of participants who report AEs or exhibit clinically significant changes during 1) 8-week treatment phase (from the first dose until the last dose), and 2) the 4-week follow up phase (to assess any lingering post treatment safety issues) will be summarized in tabular form and presented. Data permitting, exploratory analyses may be performed to evaluate the statistical significance of between-group differences (e.g. using Fisher's exact tests for adverse events, t-tests or non-parametric equivalent for changes in continuous measures) and evaluation of the effects of duration of drug exposure or drug dose on any adverse events (e.g. using exact logistic regression) and laboratory measures (e.g. using mixed effects models).

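### The safety endpoint counting participants with at least one AE has no rule for cannabis-withdrawal symptoms, so a drug effect on withdrawal can dilute or offset a toxicity difference

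*Combined protocol and SAP*

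**What the plan says.** **AE definition and capture.** Section 12.0 takes in any unfavourable, unintended sign or symptom "temporally associated with the use of a drug whether or not it is considered related to the drug". Section 12.2 elicits AEs with the SAFTEE general and specific inquiry forms, scheduled at every visit in Table 2, and adds: "All AEs will be documented, whether or not the investigator concludes that the event is related to the drug treatment". A condition present at screening is baseline, but "if the study participant's condition deteriorates at any time during the study, it will be recorded as an AE". Section 12.5 repeats this for pre-existing conditions: "the worsening or complication should be recorded appropriately as an adverse event".

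**Causality.** Section 12.3 treats the study product as always suspect. Potentially Related needs reasonable timing after dosing and allows that the participant's clinical condition contributed. Unlikely requires improbable timing, and Not Related requires a documented definitive alternative cause. An event of unknown causality is handled as related.

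**Withdrawal.** Section 11.1.2 lists the typical symptoms: "cannabis craving, anger, aggression, appetite change, weight loss, irritability, anxiety, restlessness, altered sleep, strange dreams and physical discomfort". Section 9.6.1 puts the quit date between day 3 and day 7, after dosing has begun. Section 4.2.3 (items 1 and 3) makes withdrawal an exploratory efficacy endpoint.

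**Endpoint and analysis.** Section 4.2.2 item 1 counts participants who "experience at least 1 treatment-emergent related and/or possibly related adverse event", whereas Table 10 counts those with any treatment-emergent AE. Section 14.3 tabulates this: "Group differences in the percentage of participants who report AEs or exhibit clinically significant changes". Significance tests are exploratory.

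**The concern.** Every participant is asked to attempt to quit in the first week on study drug, so a known set of unpleasant symptoms can be expected to begin after first dose in both arms. Nothing in Sections 4.2.2, 12 or 14.3 says how those symptoms are classified or tabulated.

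Two things follow. A withdrawal background common to both arms shrinks any toxicity difference in the percentage with at least one AE, because a participant already counted for withdrawal cannot be counted again for toxicity. More seriously, if the drug eases withdrawal, as Sections 3.4.4 and 3.4.10 report for the pilot study, the AE percentage falls on active drug because of efficacy. That is a bias in what the endpoint measures, and a larger sample does not remove it. The conclusion on tolerability would then partly restate the efficacy result.

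**Working it through.** **1. Do withdrawal symptoms enter the endpoint?**
- Irritability, anxiety or altered sleep starting after a day 3 to 7 quit date is an unfavourable symptom temporally associated with the drug (12.0), with onset after first dose (9.6.1). It is therefore treatment-emergent and counts under Table 10.
- For Section 4.2.2 it must also be related or possibly related. Onset within days of starting a daily drug is hard to call improbable, and a definitive alternative cause is hard to document when the drug is also suspect. The wording of 12.3 steers such events to Potentially Related, so they can enter under both definitions.

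**2. The plan's own figures.** The only sizing in the documents is for the primary endpoint. Per arm, 2 × (1.960 + 0.842)² / 0.42² = 89, so 178 in total; 178 / 0.75 = 237. Both figures reproduce. No figure is given for the AE endpoint.

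**3. Inputs for an illustration.**
- b, background AE rate apart from withdrawal: 20% (assumed) or 51% (placebo rate in the two-week osteoarthritis trial, Section 3.3, so borrowed from another population).
- w, withdrawal-AE rate on placebo: not in the documents; shown from 0 to 76%. The upper value borrows Section 2.5 ("About 76% of daily cannabis users who abruptly discontinue the use of cannabis report sleep disturbance"), which is not an AE rate.
- x, participants on active drug with a drug-caused AE: 15% (assumed).
- Relative reduction in withdrawal AEs on active drug: none or 20% (assumed).
- The three sources of AEs are taken as independent.

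**4. Formulas.**
- Placebo rate = 1 − (1 − b)(1 − w).
- Active rate, no effect on withdrawal = 1 − (1 − b)(1 − w)(1 − x), so the difference is (1 − b)(1 − w)x.
- Active rate, 20% reduction = 1 − (1 − b)(1 − 0.8w)(1 − x).

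**5. Active minus placebo, percentage points.**

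| w | b = 20%, no effect on withdrawal | b = 20%, 20% reduction | b = 51%, no effect on withdrawal | b = 51%, 20% reduction |
|---|---|---|---|---|
| 0 | +12.0 | +12.0 | +7.4 | +7.4 |
| 30% | +8.4 | +4.3 | +5.1 | +2.6 |
| 50% | +6.0 | −0.8 | +3.7 | −0.5 |
| 76% | +2.9 | −7.5 | +1.8 | −4.6 |

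Example, b = 20% and w = 50%: placebo 1 − 0.80 × 0.50 = 60.0%; active with the reduction 1 − 0.80 × 0.60 × 0.85 = 59.2%.

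**6. Where the two effects cancel.** Set 1 − w = 0.85(1 − 0.8w). Then 0.15 = 0.32w and w = 47%, whatever the background. Equivalently, the relative reduction in withdrawal AEs that cancels a 15% toxicity is 41% at w = 30%, 18% at w = 50% and 5.6% at w = 76%.

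**7. Sensitivity without any withdrawal AEs.** With 118 per arm (237 / 2) and a two-sided Fisher test at 0.05, power for x = 15% is 50% at b = 20% (20% vs 32%) and 17% at b = 51% (51.0% vs 58.4%).

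**The case against.** **The text does not name withdrawal.** All-causality capture is ordinary good practice, and Section 12 mentions neither withdrawal nor cannabis use. That stands: the gap is the missing classification and tabulation rule, not the capture. A reader might infer from 12.2 and 12.5 that increased cannabis use is recorded as an AE. That would require stretching the deterioration clauses to cover consumption, which the documents do not do; they treat use through the primary endpoint and an interim stopping criterion (8.4).

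**The rate is unknown.** A reader might infer from the 76% that withdrawal overwhelms the endpoint. The documents do not support this. The figure is sleep disturbance on abrupt discontinuation, while Section 9.6.5 accepts a reduction of at least 50% lasting a day as a successful quit attempt. Section 2.6.1 says only about half reach two weeks of abstinence even with the best behavioural combination.

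**The evidence for a drug effect is limited.** Pilot withdrawal differences survived correction only on the first two treatment days (3.4.4), and Section 3.4.9 reports no difference in minor AE rates between groups. The 20% reduction is therefore an assumption.

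**The composite is already blunt and is not the only safety measure.** At a 51% background its power is low before withdrawal enters, and 14.3 tests are exploratory. Both points stand, but a between-arm bias also affects a descriptive table. Event terms, dates and seriousness are recorded, and laboratory, vital-sign, ECG and C-SSRS endpoints and DSMB review are separate. So the documents do not support reading this as toxicity being hidden from the trial as a whole.

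**Withdrawal-like symptoms on a CNS-active drug must count as AEs.** Agreed; the fix keeps them in.

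**Conclusion.** The concern holds in a limited form. Followed as written, the plan lets withdrawal symptoms into a named secondary safety endpoint under either of its two definitions and provides no way to separate them, although withdrawal is also an efficacy outcome.

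With 15% toxicity and a 20% relative reduction in withdrawal AEs, both assumed, the two effects cancel at a withdrawal-AE rate near 47%. At 30% the observed difference is about a third of its undiluted value (4.3 of 12.0 points, or 2.6 of 7.4). If the drug does not affect withdrawal there is dilution only, by the factor 1 − w, and no reversal. These results also assume independence and depend on a withdrawal-AE rate that the documents do not supply, so they show what can happen, not what will.

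The consequence is confined to the composite percentage. It is worth correcting because that percentage is a stated basis for the tolerability conclusion and the correction is cheap.

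**What to change.** - **Section 12.2:** keep all-causality capture unchanged. Before unblinding, fix a list of withdrawal terms drawn from 11.1.2, and flag AEs on that list that start or worsen relative to the pre-dose SAFTEE assessments in Table 2.
- **Section 14.3:** report the AE percentage by arm in three rows: overall, without flagged events, and flagged events alone.
- **Section 4.2.2 and Table 10:** state one definition of the AE endpoint (related or possibly related, or any treatment-emergent) and use it in both places.

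The cost is a short term list, one flag that can be derived from recorded terms and dates, and two extra table rows. The downside is that a drug effect resembling withdrawal, such as insomnia, sits in the flagged row, so all three rows must be shown and the unflagged row must not stand alone as the safety result.
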